Replace all previous version(s) of the protocol with this revised protocol and please provide a copy of this revised protocol to all study personnel under your supervision, and archive the previous versions.

DOCUMENT HISTORY

Document	Date of Issue	Summary of Change
Revised Protocol 06	12-Aug-2015	Incorporates amendment 15
Amendment 15	12-Aug-2015	
Protocol amendment is being implemented to provide modifications to the protocol based on recommendations of the study's independent Data Monitoring Committee (DMC).
 
The DMC for the CA209025 study convened on 17-Jul-2015 to evaluate data from a planned, formal Interim Analysis of overall survival (OS). The DMC declared superiority for OS in subjects receiving nivolumab as compared to everolimus.
 
As a result of the DMC assessment, this protocol amendment is being implemented to provide a mechanism for eligible subjects randomized to the everolimus treatment Arm B to receive subsequent nivolumab therapy as part of a nivolumab extension phase.
 
Protocol amendment also indicates that the interim analysis results should now be considered the final primary analysis results of the protocol.
 
Protocol amendment also indicates the assignment of [name] and [name] as the BMS Study Directors.

Revised Protocol 05	02-Apr-2015	Incorporates amendment 14
Amendment 14	02-Apr-2015	Updated Section 5.3.1 to include language that allows the potential for the collection of additional survival data.
Revised Protocol 04	24-Dec-2014	Incorporates amendment 13
Amendment 13	24-Dec-2014	
Updated Section 4.1.3 to refer to the current Investigator Brochure for nivolumab preparation information.
 
Clarification added to Section 6.1 and 6.4 indicating SAE and pregnancy forms are to be submitted within 24 hours of awareness of the event.
 
Clarification indicating SAEs for subjects who were randomized but never received study treatment need to be reported for a period of 30 days from date of randomization.

Revised Protocol 03	27-Aug-2014	Incorporates amendment 12
Amendment 12	27-Aug-2014	
Changed the order of secondary objectives throughout document to indicate that ORR will be first and PFS second
 
Definition of PFS updated to include investigator assessed RECIST 1.1 or clinical progression
 
Updated nivolumab preparation information in Section 4.1.3 regarding filter size, acceptable diluents and IV components and minimal drug concentration

Revised Protocol 02	11-Jun-2013	Incorporates amendment 09

Document	Date of Issue	Summary of Change
Amendment 09	11-Jun-2013	
CA209025 protocol is additionally identified as “CheckMate 025, CHECKpoint pathway and nivoluMab clinical Trial Evaluation”
 
Approved generic name “nivolumab” for BMS-936558 has been added throughout the document.
 
Clarification of 4th secondary objective added
 
Information on Opportunistic Infections added to Summary of Safety
 
Clarifications added to Inclusion criteria 2e and 2h and Exclusion criteria 2h and 2k
 
Section 3.4.1 added clarification regarding palliative radiation and added information regarding palliative surgical resection.
 
Added clarifying information on subject follow-up in section 3.6
 
Updated product information in Table 4.1-1
 
Added clarifying information on weight used for nivolumab dose in section 4.3
 
Added Nephrotoxicity to list of management guidelines available in IB
 
Added clarification and guidance to Tables in section 5.1, removed HCO₃, added albumin, allow for serum urea or BUN, HCV Ab or HCV RNA and added additional sample collections to Table 5.1-6
 
Clarifying information added to section 5.3 Safety Assessments
 
Added Section 5.3.1 - Follow-up and Survival Procedures; including addition of EQ5D collection during the survival follow-up period.
 
Section 5.4 added clarification regarding bone scans.
 
Section 5.6 added clarifications throughout and information on PBMC and Peripheral Blood RNA
 
Clarification/update to section 8.2 (Population for Analysis), 8.3(Endpoints), 8.4.2.2 (Methods for Secondary Endpoints), 8.45 (Biomarker Analyses)
 
Section 9.3 updated to reflect criteria for Signatory Investigator
 
Reference 50 & 51 added
 
Additional minor clarifications and grammatical corrections made throughout document

Revised Protocol 01	05-Mar-2013	Incorporates amendment: 07
Amendment 07	05-Mar-2013	
Update to the Summary of Safety section to include new preliminary reproductive toxicology data that was distributed as a Non-clinical Expedited Safety Report and to include changes to the guidance on contraception.
 
Tables were renumbered per new model template
 
Section 3.3.1 Inclusion criteria 3a and 3d were updated to add clarifying language for length of time of contraceptive use.
 
Update Appendix 3 - Guide on Contraception

Original Protocol	18-Jun-2012	Not applicable

SYNOPSIS

Clinical Protocol CA209025

Protocol Title: CA209025: A Randomized, Open-Label, Phase 3 Study of Nivolumab (BMS-936558) vs Everolimus in Subjects with Advanced or Metastatic Clear-Cell Renal Cell Carcinoma Who Have Received Prior Anti-Angiogenic Therapy (CheckMate 025, CHECKpoint pathway and nivolumab clinical Trial Evaluation)

Investigational Product(s), Dose and Mode of Administration, Duration of Treatment with Investigational Product(s): Nivolumab dosed intravenously over 60 minutes at 3 mg/kg every 2 weeks or everolimus, 10 mg daily continuous oral dose, until disease progression, unacceptable toxicity or other reasons specified in the protocol.

[figure not shown]
Study Phase: 3

Research Hypothesis: Treatment with nivolumab will improve overall survival (OS) when compared to everolimus in subjects with advanced or metastatic renal cell carcinoma who have received prior anti-angiogenic therapy.

Objectives: To compare the clinical benefit, as measured by the duration of OS, provided by nivolumab vs everolimus in subjects with advanced or metastatic renal cell carcinoma who have received prior anti-angiogenic therapy.

Study Design: This is a Phase 3, randomized, open-label study of nivolumab vs everolimus in subjects with advanced or metastatic RCC with a clear-cell component who have received at least one but not more than two prior anti-angiogenic therapy regimens in the advanced or metastatic setting and no more than three total prior systemic treatment regimens in the advanced or metastatic setting. Subjects must have evidence of progression on or after the last treatment regimen received and within 6 months prior to study enrollment. Approximately 822 subjects will be randomized 1:1 and stratified by region (US/Canada vs W. Europe vs Rest of World), Memorial Sloan-Kettering Cancer Center (MSKCC) risk group (favorable- vs intermediate- vs poor-risk; see [Appendix 1](#)), and number of prior anti-angiogenic therapy regimens in the advanced or metastatic setting (1 vs 2) to receive nivolumab (3 mg/kg IV every 2 weeks) on Arm A or everolimus (10 mg po daily) on Arm B. No dose increases or reductions will be allowed for nivolumab. Dose modifications for everolimus will be allowed as per the approved product label or as per standard practice in countries where everolimus is not approved for the treatment of advanced RCC. Subjects will be assessed for response (RECIST 1.1) by CT or MRI beginning 8 weeks after randomization and continuing every 8 weeks for the first year and then every 12 weeks until progression or treatment discontinuation, whichever occurs later. Subjects on both arms will be allowed to continue study therapy after initial investigator-assessed RECIST 1.1-defined progression if they are assessed by the investigator to be deriving clinical benefit and tolerating study drug. Such subjects must discontinue study therapy when further progression, as defined in the protocol, is documented. The primary endpoint of this study is OS. The final analysis of OS will occur after approximately 569 events (ie, deaths) have occurred. An interim analysis of OS will occur when at least 398 OS events (70% of total OS events needed for final analysis) have occurred. Objective response rate (ORR) and progression-free survival (PFS), each based on investigator assessments using RECIST 1.1 criteria, are key secondary endpoints that will be subject to hierarchical testing, with testing for ORR followed by testing for PFS if appropriate. Other secondary endpoints include duration of objective response, evaluation of PD-L1 as a predictive biomarker for OS, incidence of adverse events, serious adverse events, and specific laboratory abnormalities, and time to disease-related symptom progression rate.

Figure 1: Trial Design Schema

*Treatment beyond initial investigator-assessed RECIST 1.1-defined progression will be considered in subjects experiencing investigator-assessed clinical benefit and tolerating study therapy. Such subjects must discontinue therapy when further progression is documented.

Amendment 15 Update:

[figure not shown]
Subjects currently receiving treatment with nivolumab will continue to be treated and monitored as specified in the protocol.

With this amendment, all subjects randomized to the everolimus treatment (Arm B) who meet eligibility criteria may enter the nivolumab extension phase, according to the schema below. These subjects will follow the assessment schedules outlined in [Tables 5.1-7](#) and [5.1-8](#) of the protocol.

Subjects treated with everolimus who have ended study treatment will be able to receive treatment with nivolumab via the extension phase of the study, assuming eligibility criteria are met (including a 14-day washout period for prior systemic anti-cancer therapy). Details are provided in [Sections 3.3.1.1](#) and [3.3.2.1](#).

Subjects currently receiving treatment with everolimus may continue to be treated and monitored as specified in the protocol as long as they are continuing to derive benefit from everolimus in the judgment of the investigator. These subjects may receive nivolumab once they are discontinued from everolimus therapy, assuming basic eligibility criteria are met (including a 14-day washout period from the last dose of everolimus).

Nivolumab Extension Phase (schema for those previously randomized to everolimus):

*Treatment beyond investigator-assessed RECIST 1.1-defined progression may be considered for subjects meeting criteria according to [Section 4.3.6](#). Treatment beyond progression for subjects in the nivolumab extension phase must be approved by the BMS Medical Monitor or Study Director prior to subjects receiving additional study drug. Criteria for discontinuation of treatment beyond progression are described in [Section 4.3.6](#).

Study Population:

Key Inclusion Criteria include:

- 1) Men and women \geq 18 years of age with histologic confirmation of advanced or metastatic RCC with a clear-cell component.
- 2) Measurable disease (as defined by RECIST 1.1).
- 3) Must have received at least one but not more than two prior anti-angiogenic therapy regimens in the advanced or metastatic setting. Prior cytokine therapy (eg, IL-2, IFN- α), vaccine therapy, or treatment with cytotoxics is also allowed. Must have received no more than three total prior systemic treatment regimens in the advanced or metastatic setting and must have evidence of progression on or after the last treatment regimen received and within 6 months prior to study enrollment.
- 4) Karnofsky Performance Score (KPS) \geq 70%.
- 5) Tumor tissue (archival or recent acquisition), FFPE block or slides, must be received by the central vendor for correlative studies in order to randomize a subject to study treatment. (Note: Fine Needle Aspiration (FNA) and bone metastases samples are not acceptable for submission.)

Key Exclusion Criteria include:

- 1) Any history of or current CNS metastases. Baseline imaging is required within 30 days prior to the first dose.
- 2) Prior treatment with an mTOR inhibitor (including, but not limited to everolimus, temsirolimus, sirolimus, and ridaforolimus).
- 3) Any active known or suspected autoimmune disease. Subjects with vitiligo, type I diabetes mellitus, residual hypothyroidism due to autoimmune condition only requiring hormone replacement, or conditions not expected to recur in the absence of an external trigger are permitted to enroll.
- 4) Any condition requiring systemic treatment with corticosteroids ($>$ 10 mg daily prednisone equivalent) or other immunosuppressive medication with 14 days prior to the first dose of study drug. Inhaled steroids and adrenal replacement steroid doses $>$ 10 mg daily prednisone equivalent are permitted in the absence of active autoimmune disease.
- 5) Uncontrolled adrenal insufficiency.
- 6) Known history of testing positive for human immunodeficiency virus (HIV) or known acquired immunodeficiency syndrome (AIDS).
- 7) Any positive test for hepatitis B or hepatitis C virus indicating acute or chronic infection.
- 8) Prior treatment with an anti-PD-1, anti-PD-L1, anti-PD-L2, anti-CD137, or anti-CTLA-4 antibody, or any other antibody or drug specifically targeting T-cell co-stimulation or checkpoint pathways.

Amendment 15 Update:

Specific eligibility criteria for subjects originally randomized to the everolimus Arm B and now entering the nivolumab extension phase are included in the protocol in [Sections 3.3.1.1](#) and [3.3.2.1](#).

Study Assessments: Overall survival is the primary endpoint of the study. Subjects will be assessed for survival at each in-person study visit and every 3 months following the required in-person visits. Subjects will be assessed for response by CT or MRI beginning 8 weeks (\pm 1 week) after randomization and continuing every 8 weeks (\pm 1 week) for the first year and then every 12 weeks (\pm 1 week) until progression or treatment discontinuation, whichever occurs later. Tumor assessments will continue after treatment discontinuation in subjects who discontinue treatment for reasons other than progression.

Amendment 15 Update:

The schedule of study assessments for subjects randomized to the everolimus Arm B and now entering the nivolumab extension phase are included in the protocol in [Section 5.1](#).

Statistical Considerations:

Sample Size: The sample size is calculated in order to compare the OS between subjects randomized to receive nivolumab and subjects randomized to receive everolimus.

Approximately 569 events (ie, deaths) with an interim analysis after 398 events (70% of total OS events needed for final analysis) provides 90% power to detect a hazard ratio of 0.76 with an overall type I error of 0.05 (two-sided). The HR of 0.76 corresponds to a 32% increase in the median OS, assuming a median OS of 14.8 months for everolimus and 19.5 months for nivolumab. The stopping boundaries at interim and final analyses will be derived based on the number of deaths using O'Brien and Fleming alpha spending function.

Endpoints: Approximately 822 subjects will be randomized to the two treatment arms in a 1:1 ratio. Assuming a piecewise constant accrual rate (with a maximum rate of 63 subjects/month and an average rate of 41 subjects/month), the accrual will take approximately 20 months. The total duration of the study from start of randomization to final analysis of OS is expected to be 42 months (20 months of accrual + 22 months of follow-up).

Analyses: If superiority in OS is demonstrated, a hierarchical hypothesis testing approach for the key secondary endpoints will be used to preserve a study-wise type I error rate at 0.05. The key secondary endpoints will be tested in the following hierarchical order:

- 1) ORR
- 2) PFS

The PFS and OS distributions will be compared via a two-sided log-rank test stratified by region, MSKCC risk group, and the number of prior anti-angiogenic regimens in the advanced or metastatic setting. The PFS/OS curves, medians, PFS rate at 6 months, OS rate at 12, 18, and 24 months for each randomized arm will be estimated using the Kaplan-Meier product-limit method. The hazard ratios (HR) and corresponding two-sided 95% CI's will be estimated in a Cox proportional hazards model using randomized arm as a single covariate, stratified by the above factors. ORR will be compared using a Cochran-Mantel Haenszel (CMH) test stratified by the same factors used above.

The OS distributions will be also estimated for each randomized arm within PD-L1 positive and PD-L1 negative subgroups separately. Similarly, hazard ratios between randomized arms will be estimated in each subgroup. Interaction between PD-L1 expression and randomized arm will also be tested in a Cox proportional model. Other exploratory analyses, such as associations between PD-L1 status and other efficacy endpoints and evaluations of different thresholds for PD-L1 positivity, will also be performed.

The duration of response (CR + PR) for each randomized arm will be estimated using the Kaplan-Meier product-limit method and limited to responders only.

Summary tables will be presented on safety parameters for each treatment arm. Toxicity rates (worst CTC grade per subject) of adverse events and specific laboratory tests will be tabulated.

The disease-related symptom progression rate based on FKSI-DRS and its corresponding 95% exact CI will also be calculated by Clopper-Pearson method for each randomized arm.

Amendment 15 Update:

As a result of the DMC's positive findings at the interim, the interim analysis results will be considered the final primary analysis results of the protocol.

TABLE OF CONTENTS

TITLE PAGE	1
DOCUMENT HISTORY	3
SYNOPSIS	5
TABLE OF CONTENTS	9
1 INTRODUCTION AND STUDY RATIONALE	14
1.1 Study Rationale	14
1.2 Research Hypothesis	14
1.3 Objectives	14
1.3.1 Primary Objective	14
1.3.2 Secondary Objectives	14
1.3.3 Exploratory Objectives:	14
1.4 Product Development Background	15
1.4.1 Nivolumab (BMS-936558) Mechanism of Action	15
1.4.2 Renal Cell Carcinoma: Background and Standard Treatments	17
1.4.3 Treatment of Advanced or Metastatic Renal Cell Carcinoma After Prior Anti-Angiogenic Therapy	17
1.4.4 Nivolumab (BMS-936558) in Renal Cell Carcinoma	18

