The primary analysis of survival was planned to be conducted after approximately 569 subjects have died (approximately 42 months from start of randomization). One interim analysis was planned after at least 398 subjects had died. As a result of DMC's positive findings at the interim, the interim analysis results with 398 death events will be considered the final primary analysis results of the protocol. Additional survival follow-up may continue for up to 5 years from the primary analysis of survival. The study will end once survival follow-up has concluded.

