8 STATISTICAL CONSIDERATIONS

8.1 Sample Size Determination

The sample size is calculated in order to compare the overall survival (OS) between subjects randomized to receive nivolumab and subjects randomized to receive everolimus.

Approximately 569 events (ie, deaths) with an interim analysis after 398 events (70% of total OS events needed for final analysis) provides 90% power to detect a hazard ratio (HR) of 0.76 with an overall type I error of 0.05 (two-sided). The HR of 0.76 corresponds to a 32% increase in the median OS, assuming a median OS of 14.8 months for everolimus and 19.5 months for nivolumab. The stopping boundaries at interim and final analyses will be derived based on the number of deaths using O'Brien and Fleming α spending function. It is projected that an observed hazard ratio of 0.845 or less, which corresponds to a 2.7 months or greater improvement in median OS (14.8 mo vs 17.5 mo), would result in a statistically significant improvement in OS for nivolumab at the final OS analysis.

Approximately 822 subjects will be randomized to the two arms in a 1:1 ratio. Assuming a piecewise constant accrual rate (with a maximum rate of 63 subjects/month and an average rate of 41 subjects/month), the accrual will take approximately 20 months. The total duration of the study from start of randomization to final analysis of OS is expected to be 42 months (20 months of accrual + 22 months of follow-up).

Table 8.1-1 summarizes the expected timing of each analysis.

Table 8.1-1: Schedule of Analyses		
	Interim Analysis	Final Analysis
Conditions	at least 398 OS events	569 OS events
Expected timing	30 months (20 months of accrual + 10 months of follow-up)	42 months (20 months + 22 months of follow-up)
Alpha level	Interim OS projected at 0.0148 level ^a	Final OS analysis projected at 0.0455 level ^a

^a Using O'Brien and Fleming alpha spending function in case exact 398 OS events are observed at the interim OS analysis.

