8.4.2.1 Methods of Primary Endpoint

The OS distributions will be compared in two randomized arms at the interim and final analyses via two-sided, log-rank tests, stratified by region, MSKCC risk group, and number of prior anti-angiogenic therapy regimens in the advanced or metastatic setting. The interim analysis for OS is planned after 398 deaths have been observed. This formal comparison of OS will allow for early stopping for efficacy and the stopping boundaries will be derived based on the O'Brien and Fleming alpha spending function in EAST v5.4. If the analysis is performed exactly at 398 events, the study could be stopped by the DMC for efficacy if the p-value is ≤ 0.0148 . The nominal significance level for the final look of OS after 569 events would then be 0.0455. The OS curve, median and OS rates at 12, 18, and 24 months for each randomized arm will be estimated using the Kaplan-Meier product-limit method. Two-sided, 95% confidence intervals for median OS will be computed by Brookmeyer and Crowley method.⁵³ Similarly, two-sided, 95% confidence intervals for OS rates at 12, 18, and 24 months will be computed by Greenwood method. The hazard ratio (HR) and corresponding two-sided 100(1- α)% (adjusted for the interim analysis) CI will be estimated in a Cox proportional hazards model using randomized arm as a single covariate, stratified by the above factors.

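### The synopsis puts a 95% CI on the OS hazard ratio while Section 8.4.2.1 requires an interim-adjusted CI, and with the interim now final the two differ materially in width

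*Protocol*

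**What the plan says.** The Analyses part of the synopsis treats PFS and OS together. After describing the stratified log-rank comparison and the Kaplan-Meier estimates for both, it says: "The hazard ratios (HR) and corresponding two-sided 95% CI's will be estimated in a Cox proportional hazards model". No adjustment for the interim look is mentioned.

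The body separates the two endpoints. Section 8.4.2.1 gives the OS hazard ratio a two-sided interval at 100(1-α)%, "adjusted for the interim analysis) CI will be estimated in a Cox proportional hazards model using randomized arm as a single covariate". Section 8.4.2.2 gives the PFS hazard ratio a 95% interval. Section 8.4.2 likewise exempts OS from the general 0.05 level.

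The OS levels are in Section 8.4.2.1. At exactly 398 deaths, "the study could be stopped by the DMC for efficacy if the p-value is ≤ 0.0148". For the later look, "The nominal significance level for the final look of OS after 569 events would then be 0.0455".

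Amendment 15 changed which look counts. Section 3.1 now reads: "the interim analysis results with 398 death events will be considered the final primary analysis results of the protocol". The synopsis carries the same update at the end of its Analyses part, but its sentence on the 95% intervals still stands. The document history and Section 3.1 record that the DMC declared OS superiority at this interim.

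**The concern.** Both statements are current text, and they prescribe different confidence levels for the hazard ratio of the primary endpoint. The body draws the line between OS and PFS deliberately; the synopsis removes it by printing a specific level for both.

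Before Amendment 15 this had little practical effect, because the final-look level of 0.0455 corresponds to a 95.45% interval. With the interim as the final primary analysis, the level that matches the OS test is 0.0148, and the gap is no longer small. A reader of the synopsis would expect an interval noticeably narrower than the one that matches the sequential test. With two levels in the protocol, either could be presented as pre-specified after the result is known.

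**Working it through.** **Inputs.** Sections 8.1 and 8.4.2.1: 398 deaths at the interim and 569 at the final look, 1:1 allocation, overall two-sided α 0.05, O'Brien-Fleming-type spending, nominal levels 0.0148 and 0.0455, critical hazard ratio 0.845 at the final look. Assumption: SE(log HR) = 2/√(deaths), which holds approximately under 1:1 allocation; stratification would shift the figures slightly.

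**1. The plan's own figures.** Lan-DeMets O'Brien-Fleming-type spending with 0.025 per side gives a one-sided interim spend of 2[1 − Φ(2.2414/√t)].
- At t = 0.70 this is 0.00738, so the two-sided level is 0.01477, which rounds to the stated 0.0148. At exactly 398/569 = 0.6995 it is 0.01472, so the printed value comes from the nominal 70%.
- The matching final level is 0.0455, as stated.
- The final critical hazard ratio is exp(−2 × 2.000/√569) = 0.8456, against 0.845 stated.
- Two-look power at hazard ratio 0.76 is 90.2%, against 90% stated.

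The design figures reproduce; the problem lies only in the interval wording.

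**2. Interval width at 398 deaths.** SE = 2/√398 = 0.1003. The half-width on the log scale is z × SE. Limits are shown for an illustrative observed hazard ratio of 0.76, computed as 0.76 × exp(± half-width).

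| Reading of the CI level | z | Half-width | Limits at HR 0.76 |
|---|---|---|---|
| Synopsis, 95% | 1.960 | 0.196 | 0.624 to 0.925 |
| α as the final-look 0.0455, 95.45% | 2.000 | 0.201 | 0.622 to 0.929 |
| α as the interim 0.0148, 98.52% | 2.437 | 0.244 | 0.595 to 0.970 |

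With z = 2.439, from t = 398/569, the last half-width is 0.245. The ratio 1.960/2.437 = 0.80, so the synopsis interval is about 20% narrower than the one matched to the interim test.

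**3. The same comparison at 569 deaths.** The ratio 1.960/2.000 = 0.98, a 2% difference. A 95% interval would exclude 1 below a hazard ratio of 0.848, and the boundary is 0.846. The mismatch becomes material only because the interim is now final.

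**4. A property of the design.** At 398 deaths a 95% interval excludes 1 for any hazard ratio below exp(−0.196) = 0.822, while p ≤ 0.0148 needs exp(−0.244) = 0.783 or less. Between these values the two rules disagree. At 0.80, for example, p = 0.026, the 95% interval is 0.657 to 0.974 and the 98.52% interval is 0.627 to 1.021. Before the interim, the chance of landing in that window was about 16% under the design hazard ratio of 0.76.

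**The case against.** A reader might infer from step 4 that the reported 95% interval could exclude 1 although the OS boundary was not met. The documents do not support that for this result. The interim became final because the DMC declared OS superiority. If it applied the stated p ≤ 0.0148 rule, both intervals exclude 1 and only their width differs. The 0.783 to 0.822 window describes the design and is not a live outcome.

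Four further points limit the concern:
- The interval decides nothing. OS is judged by the stratified log-rank p-value against the boundary, and entry to ORR and PFS testing depends on OS significance. Type I error, the stopping decision and the hierarchy are unaffected. The DMC met on 17-Jul-2015, before this revision of 12-Aug-2015.
- Section 8.4.2.1, the detailed methods section, already gives the adjusted rule, and the synopsis may simply have dropped a qualifier.
- A 95% interval is not a wrong 95% interval for being narrower. It is not the interval that the methods section asks for.
- The figure 98.52% is an inference, because Section 8.4.2.1 does not say which α sets the CI.

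All of this stands as a limit on the consequence, but it does not remove the contradiction. The synopsis prints a definite level that differs from the body. The unspecified α is itself a reason to settle the wording, since reading it as the final-look level would give an interval close to the synopsis one.

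**Conclusion.** The point holds as an internal contradiction on how the primary estimate is reported. The synopsis gives the OS hazard ratio an unadjusted 95% interval; Section 8.4.2.1 requires an interim-adjusted one. At 398 deaths the log-scale half-widths are 0.196 and about 0.244, so the synopsis interval is about 20% narrower than the one matching the sequential test. It does not call the OS conclusion into question.

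This rests on three assumptions: that α in Section 8.4.2.1 means the nominal level of the analysis reported; that the count was 398, whereas Section 8.1 sets the trigger at 398 or more; and the approximate standard error above. That both intervals exclude 1 rests on the DMC having used the stated rule, since the documents give no observed p-value or hazard ratio. The contradiction itself needs none of these.

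**What to change.** - In the synopsis, limit the 95% interval to the PFS hazard ratio and refer the OS hazard ratio to Section 8.4.2.1.
- In Section 8.4.2.1, state that α for the OS interval is the nominal level of the analysis reported, recomputed for the actual number of deaths. At exactly 398 deaths and level 0.0148 this gives 98.52%.
- If a 95% interval for the OS hazard ratio is also shown, label it descriptive.

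The cost is wording and a somewhat wider headline interval. No test, boundary or data collection changes.
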